1. INTRODUCTION

This document is a protocol for a human research study. The purpose of this protocol is to ensure that this study is to be conducted according to ICH GCP guidelines (CRF 21 Part 312), applicable government regulations and Institutional research policies and procedures.

2. BACKGROUND

2.1 Background Prevalence of Research Topic

Alcohol use disorder (AUD) remains a critical public health problem and requires more efficacious behavioral and pharmacologic treatments. Existing behavioral and pharmacologic treatments have major limitations. Currently approved medications have only modest efficacy and are therefore underutilized. They have only small to moderate effect sizes and are limited by availability, while behavioral treatments have limited access and adherence. Neither behavioral nor pharmacologic treatments by themselves are likely to provide maximal/optimal outcomes. While pharmacotherapies can be effective as long as medications are provided, they may lose effectiveness after discontinuation of treatment, whereas neurocognitive training interventions such as AABM have been shown to have more lasting effects. New treatments are needed – in particular, treatments that could lead toward combinations of behavioral interventions and pharmacotherapy.

The project will conduct a pilot human laboratory feasibility study of alcohol approach bias modification as a potential treatment in heavy-drinking individuals. The purpose of the trial is to assess and establish the feasibility of conducting controlled trials of AABM in human laboratory alcohol drinking studies. The pilot data and feasibility demonstration will allow for future funding proposals to be submitted to allow larger studies of AABM alone and combined with pharmacotherapy for AUD.

Importantly, early clinical studies by other investigators have shown that Alcohol Approach Bias Modification (AABM) training may reduce relapse to alcohol use in patients with AUD who have already stopped drinking.

One potential AUD treatment modality is to reduce automatic alcohol approach tendencies through alcohol approach bias modification (AABM) training. AABM has effects on reducing alcohol use and relapse to AUD. However, few treatment trials have been conducted with AABM and little is known about its efficacy in reducing drinking in human laboratory alcohol consumption, especially in non-treatment-seeking, heavy-drinking individuals.

2.2 Prior Experience

2.2.1 Clinical Experience

Behavioral and neural correlates of implicit alcohol-approach behavior

Patients with substance use disorders exhibit an automatic tendency to approach rather than to avoid drug cues^{1,2,3-6}. The associative process central to alcohol-approach behavior can be measured with a relatively new joystick task called the Approach-Avoidance Task (AAT) developed by Rinck et al. (2007)⁶. Differences in pulling an image toward one vs. pushing it away in relation to the content (e.g., alcohol pictures) are interpreted as automatic action tendencies⁷. Responses to appetitive cues typically occur outside of awareness⁸. The alcohol AAT taps implicit automatic approach tendencies⁹⁻¹¹. To assess implicit responding or unconscious bias¹², participants are asked to respond to an irrelevant feature of the picture – its format (left- or right-tilt) rather than to the alcohol or non-alcohol content of the picture (explicit responding). The first study of alcohol approach-bias using the AAT was conducted by Wiers et al., (2009)¹². In this study, heavy drinking students exhibited an alcohol approach-bias toward alcohol but not to generally positive/negative pictures (e.g., people and animal images)¹².

Modification of implicit alcohol-approach tendency: Alcohol Approach Bias Modification

Implicit alcohol approach-bias is related to changes in the motivational system in alcohol dependence and in heavy drinkers. Implicit alcohol-approach bias represents a target for clinical intervention. Wiers et. al., (2010)¹³ adapted the implicit alcohol AAT to be used as an intervention by manipulating the percentage of pictures of alcohol or soft drinks, which were to be pulled or pushed. To train participants to avoid alcohol, 90% of the alcohol pictures were presented in push-format and 90% of the soft-drink pictures were presented in pull-format. Wiers et. al., (2010)¹³ demonstrated that this alteration in task resulted in reductions in alcohol approach-bias (measured with the original implicit alcohol AAT), and in reduced drinking behavior in “hazardous drinkers” (not AUD) compared to those who were trained to approach-alcohol. This was the first study to show that retraining automatic approach processes could help to regain control over addictive impulses. A training version of the implicit alcohol AAT, named Alcohol Approach Bias Modification (AABM), has been studied in a handful of RCTs targeting alcohol dependent patients in in-patient treatment settings.

RCTs of Alcohol Approach Bias Modification

The first randomized controlled trial of AABM for alcohol was completed by Wiers et. al.(2011)¹⁴. An inpatient cohort of 214 AUD patients (not active heavy drinkers) were assigned to one of two experimental conditions; an explicit and implicit condition in which they were trained to make avoidance movements (pushing joystick) or to one of two control conditions in which they received sham or no training. Results showed successful alcohol approach-bias modification¹⁴.

Furthermore, clinical outcomes were obtained from 87% of the patients one year later. Patients in the experimental condition showed better treatment outcomes; only 46% of the experimental group relapsed (resumed drinking >2 days) vs 59% of the control group¹⁴. Eberl et al,¹⁵ extended the AABM work to determine the optimal amount of training needed to maximize the change in alcohol approach bias. Based on these responses, the recommended number of training sessions is 6, 9, or 12, dependent on resources¹⁵. We will provide 6 sessions over 2 weeks.

The Role of Pilot Feasibility Studies

The term 'pilot study' is widespread in clinical and translational research¹⁶. UCSF biostatistician Kraemer¹⁷, asserts that pilot studies should be conducted to assess feasibility, rather than attempt to establish the sample size for a future larger study. "Pilot studies are important in the preparation of proposals for hypothesis-testing studies," because they can "check on the availability of ... subjects using the recruitment methods proposed, "test the feasibility of the treatment and measurement protocols, train researchers, and to set up data... capabilities". The present proposal is designed to do so.

3. RATIONAL SIGNIFICANCE

3.1 Problem Statement

We will combine AABM with a human laboratory methodology of assessing alcohol consumption – the Yale Alcohol Drinking paradigm (ADP) – to assess the feasibility of these combined methods for use in future studies to test AABM efficacy in alcohol use reduction and abstinence initiation in actively drinking individuals with AUD -- not only for relapse prevention in already abstinent individuals (as previous trials have done) -- and not just to rely on self-reports of drinking/relapse behavior, but to obtain actual measures of alcohol use.

3.2 Purpose of Study/Potential Impact

We will conduct the first pilot trial of AABM effects on alcohol consumption in the human laboratory in non-treatment-seeking, heavy-drinking individuals and the first trial of AABM effects on the Yale Alcohol Drinking Paradigm - a method of rapidly assessing the potential efficacy of putative pharmacologic and possibly behavioral treatments for AUD. Participants will be 12 non-treatment-seeking heavy-drinking male volunteers. After baseline assessment, participants will undergo Human Lab session 1, in which we will administer the Alcohol Approach-Avoidance Task (AAT) (not AABM training) to measure baseline (pre-treatment) alcohol approach bias tendency, and then conduct the ADP to measure baseline alcohol consumption. After Human Lab/ADP Session 1, participants get 2 weeks of a total of 6 sessions of training; they will have been randomly assigned to undergo AABM or a sham training condition. Outcomes will be various measures of feasibility, including recruitment, retention, safety, and adverse effects and assessment of measurement burden, and the tolerability of ADP and AABM interventions

3.3 Potential Risks and Benefits

3.3.1 Potential Benefits

There is no direct benefit to these participants besides referral to treatment, which will be provided at the end of the study. They will be able to withdraw from the study at any time. The direct benefit is not great for participants, but given the potential benefit to developing effective treatments for alcoholism, the risk-benefit ratio appears favorable.

Participants may benefit somewhat from the extra physical examination, laboratory tests, and attention. In the informed consent form, participants are instructed: "Taking part in this study may not make your health better. If you are in this study, you may benefit from the physical examinations, blood tests, and review of your symptoms. Others may benefit from the overall conclusions drawn from the results of this study."

AUD is major public health problem that contributes prominently to the global burden of disease [58]. While there are several approved medications for the treatment of AUD, the available pharmacotherapies are hampered by small effect sizes, adverse effects, and limited adoption into practice. Currently available FDA-approved pharmacological agents have major limitations and there is a critical need to identify novel medication strategies for AUD treatment. Despite the large numbers of patients who suffer from AUD, medications are greatly underutilized and only a small minority of adults in the

United States who have AUD are treated with medications. *This low utilization is thought to be in part due to a perception of AUD medication ineffectiveness.* The potential knowledge to be gained in this study is judged to be highly significant. This research seeks to expand the knowledge base regarding the treatment of alcohol use disorder. Because of the known low to moderate risk profile of the study medications and the close monitoring afforded by the study design, the level of risk for prospective participants is judged to be modest, and therefore, is considered to be reasonable, in comparison with the potential knowledge to be gained.

The results of this laboratory-based drinking paradigm will provide an important initial signal regarding the potential efficacy of Alcohol Approach Bias Modification in reducing alcohol drinking. There is a great need for the development of new methods to treat alcohol use disorder. This laboratory paradigm will also provide information regarding the mechanism of action of this novel method and thus significantly contribute to the literature.

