4.3 Secondary Objectives

The Secondary Aim is to obtain a preliminary assessment of the effects of Alcohol Approach Bias Modification training on alcohol consumption and related behaviors in individuals with AUD.

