6.1.3 Method of Assignment/Randomization

All participants will receive the active AABM training intervention.

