6.1.4 Blinding and Procedures for Unblinding

Not applicable

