6.2.1 Efficacy

This is a pilot feasibility study, not an efficacy study. The primary outcome variables are measures of feasibility:

1. Time needed to recruit, screen, and run the study procedures for 12 participants.
2. Retention rates at the various in the study process (screening, Human Lab ADP session 1 + 2, AABM/sham training sessions 1-6, and follow-up).

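### With one active arm and a fixed before-then-after order (6.1.3), the study cannot give the AABM efficacy signal it promises and only partly supports controlled-trial feasibility; leftover randomisation and sham wording must be reconciled first

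*Combined protocol and SAP*

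**What the plan says.** Three statements describe what the study will deliver:

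- Section 2.1 gives the purpose as "to assess and establish the feasibility of conducting controlled trials of AABM in human laboratory alcohol drinking studies".
- Section 3.3.1 says that the laboratory results "will provide an important initial signal regarding the potential efficacy of Alcohol Approach Bias Modification in reducing alcohol drinking".
- Section 4.3 sets the secondary aim: to "obtain a preliminary assessment of the effects of Alcohol Approach Bias Modification training on alcohol consumption".

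The design sections read differently. Section 6.1.3 states: "All participants will receive the active AABM training intervention". Section 6.1.4, on blinding, says "Not applicable". Step 4 of section 6 fixes ADP Session 1 as the pre-training session and Session 2 as the post-training one. Section 6.4.1 rules out inferential statistics, and 6.2.1 says: "This is a pilot feasibility study, not an efficacy study".

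Other text still describes a controlled design. Section 3.2 says of participants that "they will have been randomly assigned to undergo AABM or a sham training condition". Step 6 of section 6 speaks of random assignment but names only AABM. Section 6.2.1 lists AABM/sham sessions among the retention points. In 6.3.5 the visit table schedules AABM/sham training, and the physician review refers to readiness for randomisation.

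**The concern.** If every man is trained, and the untrained session always precedes the trained one, session order and training are the same variable. A fall in drinks could come from training, from having already been through the drinks-or-money choice once, or from whatever else changes over the intervening weeks. The data cannot tell these apart, and a lack of change is equally ambiguous.

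The wording matters because section 2.1 intends the pilot data to support proposals for larger studies, and 3.3.1 judges the participants' risk reasonable against the knowledge to be gained. The plan's own background shows why a comparison group is needed. In the inpatient randomised trial summarised in 2.2.1, 46% of trained patients and 59% of controls relapsed. So 100 − 59 = 41% of controls did not relapse. Without controls, the whole 100 − 46 = 54% in the trained group could have been credited to training. That trial had a different population and outcome, so it illustrates the principle only.

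**Working it through.** The plan has no figure to reproduce: 6.4.2 declines any sample-size reasoning, and no SD or effect size is given.

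**1. Which design is operative?** The sections dedicated to assignment and blinding (6.1.3, 6.1.4) describe one unblinded active arm. Section 5.1 repeats the design paragraph of 3.2 without its assignment clause. Section 5.2.1 lists training sessions without sham, and the schedule (6.3.1) and payment table (6.3.5) name only AABM. Against this stand 3.2, step 6 of section 6, 6.2.1 and 6.3.5. The single arm is the better-supported reading, but the conflict is real. Steps 2 to 5 assume 6.1.3.

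**2. What the before-after change estimates.** The measure is drinks taken in two periods of four drinks, so 0 to 8. Let D1 and D2 be the counts at Sessions 1 and 2, τ the training effect, and π every other difference between the sessions. Then

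E(D2 − D1) = τ + π.

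There is one observable mean and two unknowns, so τ is not identified at any sample size. With a randomised sham arm that itself had no effect on drinking, the sham mean would estimate π and the difference between arms would estimate τ.

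**3. How an order effect would look.** Assume τ = 0, normally distributed changes with SD σ, and an order-driven fall of g × σ. With n = 12 (5.3.1), the probability that mean drinking falls is Φ(g√12), with √12 = 3.464:

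- g = 0: Φ(0) = 50%
- g = 0.25: Φ(0.866) = 81%
- g = 0.5: Φ(1.732) = 96%
- g = 0.8: Φ(2.771) = more than 99%

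The values of g are assumptions; the documents give none.

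**4. Precision is a separate matter.** The 95% half-width of the mean change is t(0.975, 11)/√12 = 2.201/3.464 = 0.64 SD of change. For assumed SDs of 2 and 3 drinks this is 0.635 × 2 = 1.3 and 0.635 × 3 = 1.9 drinks. This describes sampling error only. It shrinks as n grows; π does not.

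**5. What the single arm says about feasibility.** It informs recruitment time, retention, safety and the tolerability of the ADP and AABM. If 12 of 15 starters complete, as 5.3.1 anticipates, retention is 12/15 = 80%, with an exact 95% interval of 52% to 96%. That applies to active training only. The number of men providing data on acceptance of randomisation, sham acceptability or blinding is 0.

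**6. If a sham arm is intended.** At an assumed 6:6 split, the 95% half-width for the difference between arms is t(0.975, 10) × √(1/6 + 1/6) = 2.228 × 0.577 = 1.29 SD. The order confounding would be removed and the controlled features could be piloted, but the estimate would still be very imprecise.

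**The case against.** The strongest reply is that the plan already limits itself. The primary aims in 4.2 concern process, the outcomes in 5.2.1 are recruitment time and retention, all analyses are descriptive, and 6.2.1 disowns efficacy. The sentence in 3.3.1 is hedged, sits in a benefits narrative and governs no analysis. This stands to the extent that no data collection or planned calculation is invalid. It does not rescue 4.3, which is a declared aim phrased as an effect of training, nor does it reconcile 3.3.1 with 6.2.1.

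Some stronger readings are tempting but not supported:

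- A reader might infer that the study gives no support for controlled trials at all. Recruiting and retaining heavy drinkers and delivering both procedures safely are prerequisites for such trials, and one arm informs them.
- A reader might take the absence of randomisation and sham as settled. Several sections still say otherwise. If they are current, the confounding argument falls away.
- A reader might blame regression to the mean, or participants knowing what the training is for. Selection is on 30-day reported drinking at screening (5.3.2), not on Session 1 drinks, so much of any regression could occur before Session 1. No section says that participants are told the training's purpose, and they respond to picture format rather than content.
- A reader might take the 0.64 SD half-width as the size of the bias. It is not.
- A reader might infer that a fall will be presented as an AABM effect. No section says so.

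**Conclusion.** The point holds in a limited form. On the 6.1.3 design, the efficacy claim in 3.3.1 and the effect wording in 4.3 attribute to the study a property that it lacks, and 3.3.1 conflicts with 6.2.1. The controlled-trial purpose in 2.1 is met in part: delivery of the procedures is tested, while allocation, sham and blinding are not.

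The size of the confounding cannot be derived from the documents. The 96% figure shows how readily an apparent benefit could arise, given an assumed order shift of 0.5 SD and no training effect. The conclusion rests on 6.1.3 and 6.1.4 being the operative text. If the sham wording is current, the error lies in those two sections and in a statistical section that has no by-arm summary. Some correction is needed on either reading.

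**What to change.** First decide whether there is a sham arm, and make the allocation text agree throughout.

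**If 6.1.3 stands:**

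- Remove the randomisation and sham wording from 3.2, step 6 of section 6, 6.2.1 and 6.3.5.
- In 3.3.1, replace the efficacy sentence with: *will describe laboratory drinking before and after AABM; without a control condition, change cannot be attributed to AABM*.
- In 4.3, replace the reference to effects of training with: *within-participant change from before to after training in* alcohol consumption and related behaviours.
- In 2.1, narrow the purpose to the feasibility of delivering the ADP and AABM procedures as a step towards controlled trials, and state that randomisation, sham and blinding are not tested.

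**If the sham arm is intended:** correct 6.1.3 and 6.1.4, bring 5.1 and 5.2.1 into line, and add a by-arm descriptive summary to 6.4.3.

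On the first route the cost is wording, including a narrower declared purpose and a less favourable claim for later funding applications. The second route needs an allocation method, a blinding plan and sham delivery to be specified, and would still give an imprecise comparison.

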3.3.2 Potential Risks and Procedures to Minimize Risks

The major potential risks in this study are related to administration of alcohol, blood drawing during the physical exam and the alcohol drinking period, and risks to privacy.

Alcohol

A number of medical conditions could potentially be worsened by acute alcohol administration (e.g., liver disease, cardiac abnormality, pancreatitis, diabetes, neurological problems, diabetes, and gastrointestinal disorders). During screening, the study physician will conduct a medical history and physical exam and review laboratory findings. As a result, participants with medical problems that are judged by the study physician/PI ([name]) will be excluded from the study.

Alcohol may also cause nausea in high doses; however, nausea is not expected at the dose being used in this sample of heavy drinkers. Participants will not be drinking to levels more than they typically consume in their own drinking context, and, with the exception of the priming dose, they determine the amount of alcohol consumed.

Another area of potential risk to participants under the influence of alcohol involves their safety during the experimental procedures. Although impairment of gross motor coordination in heavy drinkers is rare at the alcohol dose used in this study, all participants will be under the supervision of the experimenters to prevent possible accidents such as falls. Participants will not leave the laboratory during the self-administration procedure,

Alcohol is a reinforcing agent, which may cause changes in behavior including repetitive or excessive alcohol consumption. Because of this, the administration of alcohol to alcoholics in treatment could potentially impede the progress of their recovery. In addition, the administration of alcohol to sober alcoholics living in the community presents a possible risk of relapse. As a result, we will be recruiting non-abstinent non-treatment-seeking alcoholics in keeping with the National Advisory Council on Alcohol Abuse and Alcoholism's recent update of its 1989⁴¹ recommended guidelines on ethyl alcohol administration. At completion of the study, we will make a serious and concerted effort to link the participant with treatment for their alcohol problems. This will be done by giving the participant objective feedback about the fact that their drinking exceeds standards for avoiding hazardous drinking, providing a brief one-session motivational intervention for their drinking, and by arranging for alcohol treatment services if they are interested. In our previous and ongoing work, several participants quit drinking and many others reduced their drinking in the three months following this intervention.

******Protection against risks of alcohol challenges******

The alcohol challenges will be conducted by [name] and research staff, using methodology adopted from the Yale group, and trained by our Yale colleague, [name].

We provide a number of safeguards to reduce the risk of physical injury by supervising all sessions and having participants stay in the CRC until they are alert and do not show signs of psychomotor impairment. We also exclude participants for whom physical or psychological problems contraindicate alcohol consumption. By selecting non-treatment-seeking participants who are currently drinking heavily on a regular basis, we are not exposing participants to alcohol consumption levels that differ from their normal drinking context. Although this has not happened in the Yale group's experience, should a participant insist on leaving the research setting prematurely, we will provide transportation back to their residence. This contingency will be explicitly addressed in the consent form.

Clearly, participants are free to discontinue the experiment at any time, although we would strongly encourage them to remain in the research setting until their blood alcohol level is below .02 and alertness and psychomotor status are judged to be safe.

Because participants are not in treatment, participation in an alcohol challenge study will not interfere with efforts to achieve abstinence. At the end of the study, however, a potential benefit is that participants will be provided with a professional evaluation and treatment will be arranged if they express interest.

****Protection against the risk of heavier alcohol use, suicidality, or other medical or psychiatric problems that may arise over the course of the study****

To protect against this risk, we will do the following:

-We will closely monitor alcohol use at each visit.

-Participants will be withdrawn from the study if, in the opinion of the PI or the DSMB, there is: sustained clinically significant increase in alcohol use between ADP sessions 1 and 2, suicidal ideation consisting of suicidal intent or plan, unacceptable adverse events judged by the study physician (the PI, [name]) to be related to study interventions, or any other clinically significant medical, psychiatric, or substance use related poor outcome that makes continued study participation unsafe.

Blood and Urine Collections

Screening blood and urine collections are performed primarily as safeguards to participants and should add no risks other than those normally associated with these procedures. Participants will have approximately 8 mL or 2 tsp of blood drawn at the intake appointment to determine liver and kidney functioning, and during the self-administration portions of the study we will draw approximately 3 mL or ½ tsp of blood at each of the 2 visits. Therefore, the total amount of blood drawn during the study (17 ml or 3.5 tsp) poses minimal risk in healthy participants. We will advise participants against donating blood for six weeks following study participation.

Blood Drawing (Venipuncture) Risks

Participation in the study requires participants to have their blood drawn 3 different times over the course of study (screening and human laboratory ADP sessions 1 and 2). Having blood drawn may cause pain (common), fainting/passing out (not very often), a bruise where the needle goes in (not very often), and infection at the same place (rare).

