5.1.1 Study Duration

The study begins with a screening visit that is expected to last approximately 4 hours. If it is deemed safe for the participant to enroll in the study and they meet all eligibility criteria, then the participant will be scheduled for 2 human lab sessions, each 12 hours long. The human lab sessions will take place on Week 2 (1st human lab session) and Week 5 (2nd human lab session). After each human lab session, a study coordinator will conduct a phone visit which is estimated to take 10 minutes. In addition to the human lab sessions, participants will come to the Ft. Miley campus 3 times per week for 3 weeks to complete Alcohol Approach Bias Modification (AABM) training sessions. These computerized training sessions last 20-30 minutes and will occur during Weeks 3 and 4 of the study. A follow-up visit will be scheduled 7 days after the 2nd and final human lab session. In total, participants can expect to spend about 32 hours over the course of 6 weeks.

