6. METHODS

The study will consist of the following steps, replicating the Yale ADP methods:

- (1) Recruitment;
- (2) Pre-screening: Brief telephone or in-person to determine eligibility for full screening beginning with establishing non-treatment seeking status;
- (3) Full Screening/baseline visit: 1-3 in-person visits to obtain consent and to evaluate eligibility (e.g. to reject participants with medical conditions): participants who meet *heavy drinking criteria*, and by confirming that the individual is *non-treatment seeking*. If these criteria are met, physical examination and laboratory testing will be conducted. Eligible participants then proceed to the main part of the study, which includes participation in 2 human lab sessions and 6 AABM training sessions.
- (4) Human Lab ADP Sessions 1 and 2: There will be two sessions, Human Lab/ADP Session 1 (Pre-training), and Human Lab/ADP Session 2 (post-training). Alcohol Drinking Paradigm (ADP): After the alcohol cue-induced craving, subjects will be given the opportunity to self-administer alcohol using the ADP. (**Table 1**) Subjects are first given a moderate Priming Drink of alcohol at 11 AM, designed to raise blood alcohol to ~ 0.03 mg%, and are instructed to drink it within 5 minutes. At 1 PM, and again at 2 PM, subjects undergo two 1-hour long alcohol Self-Administration (SA) periods. For each SA period, a tray of 4 beer drinks (each containing an amount of alcohol calculated to increase blood alcohol concentration by 0.015 mg%) will be brought into the Lab room along with a "tab" sheet worth \$12. Participants are told that these 4 drinks will be available for the next 60 minutes, and they can choose to drink or keep the money; each drink will cost \$3. The money will be given by check at the end Human Lab Sessions. This monetary cost for each drink was determined to reliably reflect the trade-off between desire to drink and cost^{20,21}. **The main measure is the number of drinks consumed over the course of two 1-hour-long SA periods**. [name] at Yale University helped to develop the ADP, and it has been adopted by other prominent research groups²²⁻³³.
- (5) Phone Visits 1 and 2: After each Human Lab ADP session, a study coordinator will call the participant to check in by phone.

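### Minor: in the text available, release after the alcohol sessions turns on a check of signs only; the protocol's own .02 level is advised but is not a release condition

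*Combined protocol and SAP*

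**What the plan says.** Section 3.3.2, under the protections against the risks of alcohol challenges, makes three relevant statements.

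- The safeguard for all participants is supervision and "having participants stay in the CRC until they are alert and do not show signs of psychomotor impairment".
- For anyone who wants to go early: "should a participant insist on leaving the research setting prematurely, we will provide transportation back to their residence". It adds: "This contingency will be explicitly addressed in the consent form".
- Participants may stop at any time, but staff would "strongly encourage them to remain in the research setting until their blood alcohol level is below .02" and until alertness and psychomotor function are also considered safe.

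Earlier in 3.3.2, under Alcohol, the protocol states: "Participants will not leave the laboratory during the self-administration procedure". That sentence breaks off at a comma in the text available.

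Section 5.1.1 schedules "2 human lab sessions, each 12 hours long". Section 6, step 4, gives a priming drink at 11 AM aimed at about 0.03, and then: "At 1 PM, and again at 2 PM, subjects undergo two 1-hour long alcohol Self-Administration (SA) periods". Each period offers 4 drinks of 0.015 each. Section 6.3.5 (Measures of Alcohol Effects) has breath alcohol taken several times in each session.

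**The concern.** The sentence that advises .02 lists the level alongside alertness and psychomotor status, so the protocol treats the level as something separate from the signs. The stay rule for everyone has only the signs. No section in the text available makes a breath reading a condition of going home, and the 12 hours is a visit length, not a release rule.

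Staff who follow the stated rule could therefore release a heavy drinker who looks well but is still above .02. Establishing that alcohol can be given safely is part of the first primary aim (section 4.2), and fine-tuning the procedures is another, so the release rule deserves to be exact. The stake is participant safety after a session. No endpoint, estimate or sample size is affected.

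**Working it through.** The plan gives no figure for the alcohol level at release, so there is nothing to reproduce. The question is how often the sign check and the .02 level could disagree at the end of a session.

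**Inputs from section 6, step 4:** priming drink 0.03 at 11 AM; *n* drinks of 0.015 each between 1 PM and 3 PM, *n* up to 8.

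**Assumptions, not in the documents:** all levels, including .02, are read in g/dL; each drink raises the level by its nominal amount without delay; drinking is spread evenly and ends at 3 PM; elimination is constant at *r* = 0.010 to 0.020 per hour; the session starts at 8 AM and so ends at 8 PM (other starts are tried below).

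**Formulas**

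- Level at 1 PM = max(0, 0.03 − 2*r*)
- Level at 3 PM = level at 1 PM + 0.015*n* − 2*r*
- Hours after 3 PM to reach .02 = max(0, (level at 3 PM − 0.02)/*r*)

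**Time at which .02 is reached**

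| Drinks | *r* = 0.010 | *r* = 0.015 | *r* = 0.020 |
|---|---|---|---|
| 8 | (0.110 − 0.02)/0.010 = 9.0 h, midnight | (0.090 − 0.02)/0.015 = 4.67 h, 7:40 PM | (0.080 − 0.02)/0.020 = 3.0 h, 6:00 PM |
| 6 | (0.080 − 0.02)/0.010 = 6.0 h, 9:00 PM | (0.060 − 0.02)/0.015 = 2.67 h, 5:40 PM | (0.050 − 0.02)/0.020 = 1.5 h, 4:30 PM |
| 4 | (0.050 − 0.02)/0.010 = 3.0 h, 6:00 PM | (0.030 − 0.02)/0.015 = 0.67 h, 3:40 PM | already at .02 at 3:00 PM |

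**Who is above .02 at 8 PM?** For *r* below 0.015 the level at 8 PM is 0.03 + 0.015*n* − 9*r*. It exceeds 0.02 when *r* < (0.01 + 0.015*n*)/9.

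- 8 drinks: 0.130/9 = 0.0144
- 7 drinks: 0.115/9 = 0.0128
- 6 drinks: 0.100/9 = 0.0111
- 5 drinks: 0.085/9 = 0.0094, outside the assumed range

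At the slowest assumed rate, 0.010, the 8 PM levels after 8, 7 and 6 drinks are 0.060, 0.045 and 0.030. The further waits to .02 are 4.0, 2.5 and 1.0 hours. At 0.015 or faster, or with 5 or fewer drinks, nobody is above .02 at 8 PM.

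**Other start times.** The rate below which a man is still above .02 at the session end is:

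| Session end | 8 drinks | 7 drinks | 6 drinks | 5 drinks |
|---|---|---|---|---|
| 7 PM | 0.100/6 = 0.0167* | 0.115/8 = 0.0144 | 0.100/8 = 0.0125 | 0.085/8 = 0.0106 |
| 8 PM | 0.0144 | 0.0128 | 0.0111 | none |
| 9 PM | 0.130/10 = 0.0130 | 0.115/10 = 0.0115 | none | none |
| 10 PM | 0.130/11 = 0.0118 | 0.115/11 = 0.0105 | none | none |

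*Above 0.015 the priming drink has cleared by 1 PM, so the limit is (0.015*n* − 0.02)/6.

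The 12-hour visit therefore closes most of the gap. It does not close it for slow eliminators who take most of the drinks.

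**The case against.** The case against has several parts, and much of it stands.

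**Transport.** A reader might infer that a man without signs who leaves above .02 is owed no ride, because leaving prematurely is not defined. The documents do not support this. A man insists on leaving only when staff advise him to stay, and the next paragraph gives that advice with .02 in it. Read together, leaving above .02 is most naturally premature, and the ride applies. The term could be tied to .02 explicitly, but that is a confirmation of wording.

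**Early leavers.** At 5 PM, 8 drinks leave a level of 0.090, 0.060 or 0.040 at rates of 0.010, 0.015 and 0.020, which might suggest a large exposed group. But walking out at 5 PM from a 12-hour session is early on any ordinary reading, so transport is already promised, and no section provides for routine release at that hour.

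**The sign check.** One might infer from "impairment of gross motor coordination in heavy drinkers is rare at the alcohol dose used in this study" that men would pass the check while above .02. The remark concerns gross motor signs and falls during procedures. The stay rule also covers alertness and psychomotor signs generally, so the remark does not show how often men would pass.

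**Voluntariness.** Nobody can be held until he reaches .02, so for a man who insists on going, advice and a ride are what can be offered. This explains the wording for him. It does not explain why the level is absent from the routine rule.

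**Text not available.** The consent form, Table 1 and the rest of the broken sentence in 3.3.2 could state a release level. This stands, and it makes the point conditional.

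**Other safeguards.** Sessions are supervised and the study physician reviews safety at each visit (section 6.2.2.1). These lower the risk but set no release level.

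**Conclusion.** The point holds as a minor one about routine release. In the text available, a man may go home once he is alert and without psychomotor signs, and the protocol's own .02 level is advice only. With an assumed 8 PM end and the assumed elimination range, this matters only for men who take 6 to 8 drinks and eliminate slower than about 0.011 to 0.014 per hour. At the extreme (8 drinks, 0.010 per hour) the level is 0.060, four hours from .02.

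The size depends on the elimination rate, the unit and the session start time, none of which the documents settle. They also give no figure for how many of the 12 men, if any, would be in this group. It should not be read as a finding that the protocol lacks a release level everywhere, or that men above .02 are left without transport.

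**What to change.** In section 3.3.2, make routine release at both alcohol sessions conditional on a recorded breath alcohol below .02 together with the existing check of alertness and psychomotor signs. Add one sentence confirming that anyone who chooses to leave at or above .02 counts as leaving early and is given transport. Mirror this in the consent form if it is not already there.

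The cost is one recorded reading per session with a device already in use, and an occasional longer stay or ride. No endpoint, analysis or sample size changes. First check the consent form and Table 1: if either already states the rule, no change is needed beyond a cross-reference.
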